STUDY PROTOCOL

Exploring Predictors of Quality of Life in Older Adults with End-Stage Kidney Disease Receiving In-Center Hemodialysis: A Cross-Sectional Analysis of Sociodemographic, Dialysis-specific, Biopsychosocial, and Activity-Related Factors

Overview

The global prevalence of end-stage kidney disease (ESKD) is increasing, particularly among older adults. Maintenance in-center hemodialysis (ICHD), while life-sustaining, imposes significant treatment and symptom burdens that disproportionately affect older patients with coexisting frailty, multimorbidity, and psychosocial challenges.

While older adults with ESKD consistently prioritize quality of life (QoL) over survival, this outcome remains underrepresented in clinical research. Health-Related Quality of Life (HRQoL) measures are often used as proxies but may not fully capture what matters most to patients, especially during major transitions like dialysis initiation. Differences in HRQoL instruments also create variability in evaluations and cost-effectiveness estimates.

This study seeks to address these gaps by examining overall QoL using an individualized, validated instrument, and identifying its key determinants among older ICHD patients.

Study objectives

Primary Objective:

To identify key factors associated with overall QoL, as measured by the Amnestic Comparative Self-Assessment (ACSA) and a range of sociodemographic, dialysis-specific, biopsychosocial, and activity-related factors, in older adults receiving ICHD.

Secondary Objectives:

To examine the relationship between overall QoL (ACSA) and HRQoL instruments (EQ-5D-3L, EORTC QLQ-C30, QLQ-MY20).

To explore clusters of patients with similar QoL profiles using multivariate and cluster analysis.

Study design

Type: Observational

Model: Cross-Sectional

Time Perspective: Prospective

Reporting Guidelines: STROBE

Study population

Inclusion Criteria

Adults aged ≥65 years

Receiving maintenance in-center hemodialysis (ICHD)

Able to provide informed consent

Sufficient cognitive and language ability to complete questionnaires in Dutch

Exclusion Criteria

Undergoing ICHD due to an acute hospital admission

Formal diagnosis of severe psychiatric or cognitive disorders (e.g., dementia)

Inability to understand or respond adequately to study assessments

Study setting and recruitment

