General

Statistical analysis consists of four stages: descriptive analysis, univariate analyses, multivariate analyses, and cluster analysis. Two-tailed tests are used, with $p < 0.05$ considered statistically significant unless otherwise specified. Data distributions to be assessed for normality using the Shapiro-Wilk test. Missing data are handled using listwise deletion per questionnaire, with the assumption that missingness was random. All statistical analyses are performed using IBM SPSS Statistics version 29.0.2.0.

Stage 1: Descriptive analysis

Descriptive statistics are calculated for all demographic, clinical, functional, psychosocial, and quality of life variables. This includes:

- Overall QoL (ACSA)
- Participant demographics (age, sex, dialysis vintage, hospital setting)
- Comprehensive Geriatric Assessment (STRATIFY, Mini-Cog, GDS-4, NRS-2002, Pain VAS-scale, Questioning on vision, hearing, continence)
- Frailty score (GFI)
- ADL functioning (BIA; basic, instrumental, advanced activities of daily living)
- HRQoL scores (EQ-5D-3L, EORTC QLQ-C30, QLQ-MY20)

Stage 2: Univariate analyses

Univariate analyses are conducted to identify associations between the independent variable (ACSA) and the dependent variables (secondary outcomes).

Analyses are stratified based on variable type: Dichotomous variables: Mann-Whitney U test; Categorical variables with ≥ 3 groups: Kruskal-Wallis test; Ordinal and continuous variables: Spearman's rank correlation coefficients

Variables with a p -value < 0.05 in univariate testing are considered for multivariable modeling.

Additional exploratory analyses examine the relationship between the ACSA score and HRQoL instruments/domains, including the EQ-5D utility index.

Stage 3: Multivariate Analysis

A stepwise multiple linear regression analysis is performed to identify independent predictors of overall QoL (ACSA score). Variables significantly associated with the ACSA in univariate analysis are entered sequentially using forward selection. Multicollinearity is assessed, and variables with high collinearity were excluded.

The model is evaluated using Adjusted R² to assess the proportion of explained variance. Regression coefficients (unstandardized B), standardized beta weights, t-values, and significance levels are reported for each step.

Stage 4: Cluster Analysis

To explore subgroups of participants with distinct QoL profiles, a two-step cluster analysis is performed:

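### Stage 3 reports p-values and Adjusted R² from a model selected on the same participants, with no allowance for the search, and the planned bootstrap does not say what each resample repeats

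*Combined protocol and SAP*

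**What the plan says.** The primary objective is "To identify key factors associated with overall QoL", and the title describes the work as "Exploring Predictors of Quality of Life in Older Adults with End-Stage Kidney Disease Receiving In-Center Hemodialysis".

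The SAP selects variables in three data-dependent steps, all in the same participants:

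- **Screen (SAP, Stage 2).** Variables with p below 0.05 "in univariate testing are considered for multivariable modeling". No multiplicity adjustment is given.
- **Collinearity (SAP, Stage 3).** "Multicollinearity is assessed, and variables with high collinearity were excluded". VIF is named under Sensitivity Analyses, without a cutoff.
- **Selection (SAP, Stage 3).** "Variables significantly associated with the ACSA in univariate analysis are entered sequentially using forward selection".

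The purpose given for the regression is to find independent predictors of the ACSA score. Coefficients, t-values and significance levels are reported at each step, and Adjusted R² is the measure of explained variance. Stage 3 carries no caveat about selection.

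Sensitivity Analyses adds one sentence: robustness will be checked with different model orders and with bootstrapping. It does not say what is redone in each resample or what is reported from it.

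**The concern.** A p-value from ordinary regression assumes that the model was fixed before the data were seen. Here the variables are in the model because they did well in these data, so the reported p-values are too small for what was done. Adjusted R² has a related weakness: its penalty counts the variables retained, not those tried and discarded.

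Two things are at stake. A variable with no independent effect can be reported as an independent predictor with an unqualified p-value. The explained variance can also be overstated for the factors actually named, mainly when the sample is small or effects are weak. The retained variables may then feed the Stage 4 clustering.

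The bootstrap could address the second problem, but only if it repeats the search. A bootstrap that takes the selected model as given starts after the bias has arisen.

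**Working it through.** The plan states no sample size, expected R² or error rate for this model, so there is no planned figure to reproduce. What follows is illustration under stated assumptions.

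**1. Number of candidates.** Protocol, Outcome measures: 6 from medical records + 7 geriatric assessment items + 1 frailty score + 3 activity scores = 17 outside HRQoL. SAP Stage 1 also lists sex, hospital setting and GDS-4: 17 + 3 = 20. If the three HRQoL instruments are eligible, there are at least 23. Their eligibility is unclear, since Stage 2 says "Additional exploratory analyses examine the relationship between the ACSA score and HRQoL instruments/domains".

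**2. Screen alone, independent candidates, no true effects.** Chance that at least one passes = 1 − 0.95^k:

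- k=17: 1 − 0.418 = 58%
- k=20: 1 − 0.358 = 64%
- k=23: 1 − 0.307 = 69%

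**3. Screen plus forward selection, no true effects.** Assumptions: Spearman screen at p<0.05, forward entry at p<0.05 (the SAP's general level), correlation between candidates 0 or 0.3, n from 60 to 200. With 20 candidates, separate simulations gave at least one false predictor in 41-52%, 43-54% (n=80 to 200), 40-55% and 38-53% of studies. With 17 candidates the result lies towards the lower part of the band. About 35-55% covers both counts.

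**4. Why Adjusted R² does not repair this.** Adjusted R² = 1 − (1 − R²)(n − 1)/(n − p − 1), where p is the number of variables kept. The number searched does not appear.

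**5. Size of the R² effect.** Assume three true standardised effects of 0.2, 20 candidates, correlation 0.3 and total variance 1. The true three-factor model explains 3(0.2²) + 6(0.2²)(0.3) = 0.12 + 0.072 = 0.192. Truly explained means the R² that the selected variables would reach with their best coefficients, so estimation error plays no part.

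| n | Adjusted R² | Truly explained by selected variables | Difference | R² in new patients |
|---|---|---|---|---|
| 60 | 0.21 | 0.10 | 0.11 | 0.04 |
| 100 | 0.20 | 0.13 | 0.07 | 0.09 |
| 200 | 0.20 | 0.17 | 0.03 | 0.15 |

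Over all settings tried (effects 0 to 0.4, correlation 0 or 0.3), the difference was 0.01 to 0.11 at n=60, 0.01 to 0.07 at n=100 and 0.00 to 0.03 at n=200.

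**6. What the bootstrap would show.** Corrected R² = R² in the study − mean over resamples of (R² in the resample − R² of that resample's model in the original participants). The setting is as in step 5, plus one highly collinear pair (correlation 0.92) and a VIF>5 exclusion.

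| n | Refit selected model only | Repeat whole procedure | New patients |
|---|---|---|---|
| 60 | 0.19 | 0.06 | 0.04 |
| 100 | 0.19 | 0.10 | 0.10 |
| 200 | 0.19 | 0.14 | 0.15 |

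Refitting only is too high by 0.15, 0.09 and 0.04. Repeating the procedure is off by +0.02, 0.00 and −0.01. Across effects of 0.2 and 0.3 and both correlations, refitting only was 0.01 to 0.16 too high, and repeating the procedure ran from +0.017 to −0.035.

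Refitting also fails to flag false predictors. With no true effects, its 95% interval excluded zero for 94% (n=100) and 95% (n=200) of the falsely selected variables.

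**The case against.** **The study is exploratory and already plans a bootstrap.** Both are true, and they limit the severity. But Stage 3 speaks of independent predictors without the title's caution, and the bootstrap helps only if it repeats the search. A reader might infer that the SAP intends to refit the selected model only. The text does not say so. If the whole procedure is already meant, one sentence settles it. Trying other model orders does not remove selection bias.

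**The remedy does not cure false entry.** This stands. In the simulations, retained variables with no independent effect were reselected in 47-60% of resamples and true ones in 58-96%. The ranges overlap, so inclusion frequency cannot separate them.

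**Adjusted R² is not wrong about the explainable variance.** In the step 5 example it is close to the true model's 0.192. A reader might infer that it exaggerates how much of the ACSA can be explained at all. The calculation shows only that it exaggerates what the particular retained variables explain. Nor does it follow that a pre-specified model would predict better: one containing all 20 candidates had new-patient R² of −0.26, −0.02 and 0.10 at n=60, 100 and 200, below the stepwise model.

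**With a larger sample the gain fades.** At n=200 with effects of 0.3, refitting only was slightly closer (+0.01 to +0.02) than repeating the procedure (−0.02 to −0.03).

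**Other stronger readings fail.** The regression is not the sole answer to the primary objective, because Stage 2 also identifies associations. The entry threshold is not clearly absent, because p<0.05 unless otherwise specified is a natural reading. The count of 20 depends on adding Stage 1 items. Any effect on Stage 4 is unquantified, and the prior analyses it refers to may include Stage 2.

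**Conclusion.** The concern holds in limited form. As written, Stage 3 yields p-values that ignore the selection and an Adjusted R² that can be optimistic for the variables reported, and the one planned safeguard is too loosely described to tell whether it would show this.

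If nothing is truly related to the ACSA, roughly 35-55% of studies would name at least one false predictor. With three weak effects, the excess in Adjusted R² is about 0.11 at n=60, 0.07 at n=100 and 0.03 at n=200. These sizes rest on assumed sample sizes, effects, correlations, 17 to 20 candidates and entry at p<0.05. The direction follows from the method, and the R² effect becomes small as n or effect size grows.

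This is a cheap improvement worth making. It does not invalidate an exploratory study.

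**What to change.** 1. **Sensitivity Analyses.** Add, for example: *Each bootstrap resample of participants starts from all candidate variables and repeats the Stage 2 screen, the collinearity exclusion and the Stage 3 forward selection. A resample in which nothing is selected counts as an intercept-only model. The optimism-corrected R² is reported beside Adjusted R². Inclusion frequencies describe stability only and do not separate true from false factors.*
2. **Stage 3.** State that p-values of the selected model are descriptive and unadjusted for selection, and call retained variables exploratory factors, in line with the title.
3. **Inputs to item 1.** List the candidates (saying whether HRQoL scores are eligible), and state the entry threshold and VIF cutoff. They are needed because the resamples cannot repeat an undefined procedure.

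**Cost.** SAP wording and a short resampling script, with no new data. The SAP says "All statistical analyses are performed using IBM SPSS Statistics version 29.0.2.0", so that sentence needs a matching line if the script runs outside the SPSS menus. The reported explained variance will be less favourable and sometimes slightly over-corrected (by up to 0.035 in the simulations).

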-Hierarchical clustering using Ward's method to determine the optimal number of clusters based on the dendrogram.

-K-means clustering to define group composition using the dependent variable (ACSA) and significant independent variables identified in prior analyses.

Sensitivity Analyses

The robustness of regression findings is checked using alternative model orders and bootstrapping methods. Variance inflation factors (VIF) are used to monitor multicollinearity.

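### Re-ordering the variables cannot test a forward-selected model: one of the two named robustness checks is uninformative about which factors are chosen

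*Combined protocol and SAP*

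**What the plan says.** Stage 2 of the SAP screens each factor against the ACSA. Those with a p-value below 0.05 "in univariate testing are considered for multivariable modeling". Stage 3 then builds a stepwise multiple linear regression: "Variables significantly associated with the ACSA in univariate analysis are entered sequentially using forward selection". No entry or removal p-value is given. On output, "Regression coefficients (unstandardized B), standardized beta weights, t-values, and significance levels are reported for each step". On collinearity, "Multicollinearity is assessed, and variables with high collinearity were excluded", with no cut-off and no rule for which variable is dropped.

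The Sensitivity Analyses paragraph names two checks of the regression: "The robustness of regression findings is checked using alternative model orders and bootstrapping methods". It adds that "Variance inflation factors (VIF) are used to monitor multicollinearity". It does not define model orders, does not say what is repeated within a bootstrap resample, and sets no criterion for calling a finding robust.

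**The concern.** The primary objective is to identify the key factors associated with overall QoL, so the list of selected factors is the main result. Many candidates overlap in content: the GFI (which itself covers biopsychosocial factors), three levels of daily activity, GDS-4, pain, and possibly the HRQoL scales. Forward selection is fragile when it has to choose among overlapping predictors, and a robustness check should probe that choice.

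Re-ordering does not. Taken with the method Stage 3 states, it gives the same final model whatever the data, so agreement across orders carries no information. If the report offered such agreement as evidence of robustness, readers would be reassured on the point where the model is weakest. The reassurance could also carry into Stage 4, where the k-means clustering uses variables found significant in earlier stages.

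**Working it through.** The documents give no sample size and no figure that bears on this point, so there is nothing of the plan's own to reproduce. The central result is algebraic. The simulations illustrate it.

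**1. Fixed set of variables, different order.** Let X be the design matrix and P a permutation matrix, so the re-ordered matrix is XP. Least squares gives

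b* = (P′X′XP)⁻¹P′X′y = P′(X′X)⁻¹X′y = P′b.

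These are the same coefficients in a different order. Fitted values are XPP′b = Xb, so the residuals and R² are the same, and so is Adjusted R² = 1 − (1 − R²)(n − 1)/(n − k − 1). Standard errors come from the diagonal of s²(X′X)⁻¹, which is permuted in the same way, so t, p and the standardized betas are unchanged. VIF = 1/(1 − Rⱼ²), where Rⱼ² comes from regressing variable j on all the others; order does not enter.

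**2. Forward selection, candidates listed differently.** Each step admits the remaining candidate with the smallest p-value. The minimum over a set does not depend on how the set is listed, so, barring exact ties, every step and the final set are the same.

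**3. What does move.** If a different entry sequence is forced on the same set, the step-by-step results (B, beta, t, p and R² increments) change until the last variable is in. The plan reports these step results, but the final model is unaffected.

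**4. Numerical check.** Assumed inputs, not from the documents: n = 80, 120, 200; 8 candidates with pairwise correlation 0.3, 0.5 or 0.7; coefficients 0.3, 0.3, 0.2, 0.2, 0.1, 0.1, 0, 0; residual SD 2; outcome rounded and clipped to −5 to +5; Spearman screen at p < 0.05; entry at p < 0.05; 8 random orders and 40 bootstrap resamples per data set. Each scenario had 60 data sets, less those in which fewer than two candidates passed the screen.

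| n | correlation | data sets | forward-selected set changed | set changed, imposed sequence* | same set on bootstrap re-selection† |
|---|---|---|---|---|---|
| 80 | 0.3 | 45 | 0 | 89% | 38% |
| 80 | 0.5 | 57 | 0 | 96% | 32% |
| 80 | 0.7 | 60 | 0 | 100% | 31% |
| 120 | 0.3 | 58 | 0 | 95% | 29% |
| 120 | 0.5 | 58 | 0 | 100% | 28% |
| 120 | 0.7 | 60 | 0 | 100% | 23% |
| 200 | 0.3 | 60 | 0 | 98% | 20% |
| 200 | 0.5 | 60 | 0 | 100% | 20% |
| 200 | 0.7 | 60 | 0 | 100% | 19% |

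*Analyst-imposed sequence, each variable kept only if p < 0.05 at its own entry; see the objection. †Mean share of resamples; the screened candidates were held fixed.

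Total data sets: 45 + 57 + 60 + 58 + 58 + 60 + 60 + 60 + 60 = 518, with 0 changes under forward selection. A stepwise variant with removal at p > 0.10 also gave 0. The largest fixed-set coefficient difference was 3.8e-15. One numerical caution: when p-values closer than 1e-12 in absolute terms were treated as ties, the last scenario showed 4 changes (2 for the stepwise variant), because very small p-values then counted as equal. Comparing them on a relative scale removed all of these.

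**5. Second simulation.** Assumed inputs: 12 candidates, correlation 0.5–0.8 within domain and 0.3 between, 4 true factors, n = 75, 100, 150, 200. Over all 4! = 24 orders of 4 correlated predictors, coefficients, t-values and Adjusted R² differed by at most 4.1e-15. Shuffling the candidate list changed the selected set in 0 of 4 × 1,000 = 4,000 samples. Backward elimination on the same candidates gave a different set in 9% to 26% of samples.

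**The case against.** A reader might infer that the whole robustness section is bound to confirm the model however unstable it is. The documents do not support that, for three reasons.

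- *Bootstrapping is named in the same sentence.* If selection is repeated in each resample, it can expose instability; in the table the set failed to recur in 62% to 81% of resamples (100 − 38 and 100 − 19). This stands. But the plan does not say that selection is repeated. If only the coefficients of the model already selected are bootstrapped, selection instability is missed again.
- *The term is undefined.* If it means a sequence imposed by the analyst with a retention test at each entry, the final set can change, and did so in 89% to 100% of simulated data sets. Dropping collinear variables in a different order could also change the model, since no drop rule is given. This stands as a limit on the word cannot. However, an imposed sequence is a different procedure from the forward selection in Stage 3, and the documents describe it nowhere.
- *Step results do move, and the plan reports them.* True, but they do not bear on the final model.

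It can also be said that this is one clause in a supportive section of an observational study, that no primary estimate changes, and that no document says what the report will claim about robustness. All of that is fair. It limits the weight of the point, not its correctness.

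**Conclusion.** The point holds in limited form. Under the forward selection stated in Stage 3, re-ordering is uninformative about the final model: its effect on final coefficients, p-values, Adjusted R² and VIFs is zero, apart from rounding and exact ties. That conclusion is algebraic and needs no assumed sample size or correlation. One of the two named checks therefore cannot show whether the choice of factors is stable, and the other can do so only if selection is repeated in each resample, which the plan leaves unsaid.

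It does not follow that the plan has no means of detecting instability, or that the selected model will prove unstable. The 19% to 38%, 9% to 26% and 89% to 100% figures rest on assumed inputs. They show that selection can be unstable where re-ordering sees nothing, but they are not estimates for this study. The wording should be changed before analysis; the primary analysis itself is not invalidated by this point.

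**What to change.** Replace alternative model orders in the Sensitivity Analyses paragraph with checks that can fail:

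1. Repeat both the univariate screen and the forward selection within every bootstrap resample, and report each factor's inclusion frequency. State the number of resamples, and fix in advance the frequency at which a factor will be called stable.
2. Beside the selected model, show the model containing all candidates without selection, with 95% CIs, fitted to the same participants. Rerun the selection by backward elimination as a secondary comparison only: both procedures use one sample and the same screened candidates, so their agreement is weaker evidence than item 1.
3. State that no factor will be described as robust on the basis of re-ordering. If an imposed entry sequence with retention tests was intended, define it and say how disagreement between sequences will be judged.

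The cost is a few sentences of SAP text and some extra model runs on data already being collected. The downside is that some factors may have to be reported as not robust.
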